1. AMENDMENT HISTORY

Amendment No.	Protocol Version No.	Date issued	Author(s)	Details of Changes made
1	1.1		RM	External peer reviewer comments addressed
	1.2	18/02/18	RM	Based on further review sample size increased. Surveillance aspect moved into separate protocol.
	1.3	20/3/18	RM	Updated to reflect multisite nature of study
	1.4	12/06/19	RM	Minor clarifications and corrections
	1.5	27/11/19	RM	Adjust to allow inclusion of children on outpatient parenteral antibiotics and extension of end-date Link to University insurance certificate

Signed by Chief Investigator:

[name]

Signed by Sponsor

2. SYNOPSIS

Study Title	Quality of Life Effects of Chickenpox on Hospitalised Children and their Families.				
Internal ref. no.	QoL-PoX - hospital				
Study Design	Observational Cohort Study				
Study Participants	Children aged 0-16 years and their carers				
Planned Sample Size	100 (but to allow possible over recruitment to 200)				
Follow-up duration	Up to 6 months after hospital discharge.				
Planned Study Period	1st March-2018 1st Nov 2020 (30m recruitment+6m follow up)				
Primary Objectives	To assess the impact of varicella disease on quality of life,				
Secondary	To assess the impact of varicella disease on healthcare use, financial and health				
Objectives	impact on family unit				
Primary Outcome	- QALY loss of patients and carers				
Measures					
Secondary Endpoints	- Wider financial and health impact on family members of affected patients				
Intervention (s)	none				

3. Relevant Study Documents

- Protocol (this document)
- Consent form
- Parent Information Sheet
- Child Information Sheet
- Daily Diary Inpatient (parental proxy + young person version)
- Weekly Diary for home (parental proxy + young person version)

4. INTRODUCTION

4.1. Rationale for study and study design

4.1.1. Epidemiology and burden of disease

Varicella Zoster (VZ) or chickenpox is a ubiquitous disease of childhood. Almost all children will catch it during the first five years of life[1]. It is spread through respiratory secretions or contact with vesicle fluid. After exposure the disease has a long asymptomatic incubation period of 10-21 days[2]. Children first become infectious during a two day generalised coryzal period before the development of the characteristic exanthema. This usually lasts for around five days before all spots are crusted and the child is no longer Qol-PoX-H (IRAS 240389)

infectious. Most children will have a mild course with the only inconvenience being an unpleasant itchy rash and time excluded from childcare. However some will go on to develop secondary complications, the most common being a bacterial infection of the lesions but with other serious complications such as stroke, encephalitis or pneumonitis occurring more rarely.[3] The relative proportions of children with these complications are poorly understood in the UK and will not be adequately captured by current routine surveillance.

4.1.2. Baseline for measuring rates of disease seeing hospital care

As chickenpox is not a notifiable disease, most of our knowledge of the epidemiology comes from routinely collected data on cases reported in the UK is available from the Royal College of General Practitioners Research and Surveillance Centre by sentinel GP practices in England and Wales. Admissions directly attributed to varicella may be identified through Hospital Episode statistics. These routinely collected datasets are likely to accurately capture cases of moderate varicella (the mildest cases will not seek any medical advice) but for secondary cases of e.g. cellulitis or childhood stroke the causal link with varicella may not be made clinically thus recorded or coded. The best data on complication rates in the UK is from a 2002 BPSU surveillance study.[4] However this used a very restrictive criteria for inclusion of severe cases so only identified a case incidence of 0.82/100,000 person years. In comparison a prospective surveillance study from Belgium found 29.5/100,000 person years of which 19/100,000 were complicated.[5]

4.1.1. Recent potential changes in UK epidemiology

There is an ongoing unexplained rise in the rates of invasive Group A streptococcal (iGAS) bacterial infections.[6] Evidence suggests that chickenpox is the most common risk factor for iGAS disease in children.[7] There is also evidence that the age distribution of children with VZV is shifting to affect increasingly younger children – the cause is not known but this is possibly due to rising rates of childcare facilitating increased mixing at a younger age.[8]

4.1.2. Impact on Health Related Quality of Life

The only study quantifying the health related quality of life (HRQoL) lost due to varicella in UK children used a convenience sample of forty two children attending primary care for other reasons whose mothers were asked to recall their child's quality of life at the time they had had chickenpox.[9] This suggested that the QALY loss due to VZV was 4 per 1000 patient cases. However the impact on carer HRQoL or social costs such as time from work / healthcare were not assessed. A similar retrospective method was used in Belgium finding a QALY loss of 4 per 1000 for children not seeking medical care but 10 per 1000 for those who had been ill enough to visit their General Practitioner.[10]

The HRQoL loss of patients hospitalised with VZV has not been assessed in the UK. In our study we will also be assessing carer HRQoL which although recommended by NICE to be included in economic analyses[11] is often overlooked and in previous studies we have found to be a significant additional burden of disease.[12] Of particular interest in children hospitalised with VZV is the persistence of long term sequelae. At discharge QoL-POX-H (IRAS 240389)

Protocol Version 1.5 (27/11/201)

from hospital children are unlikely to be back to a normal health state so we plan to follow them with additional diaries weekly for one month then a final follow up at six months.

4.1.3. Potential of Vaccination to prevent disease

Safe and effective vaccines exist against varicella. These have been in use in America since 1995[13] and Australia since 2005[14] with drastic reduction in rates of disease.[15] The question of UK vaccination has been debated for over a decade.[16] However the introduction to the UK has been stalled due to concerns of the potential for a rise in the rates of shingles in adults.[17] Whilst this has not been proven in practice in other countries[15,18] it currently still dominates the cost utility analysis for the UK models. The JCVI plan to review the evidence for the introduction of varicella vaccination in the UK and have highlighted this area in particular as of need for further research and data.

5. OBJECTIVES

5.1. Primary objectives

Identify a cohort of children in hospital with acute or recent chickenpox (within 21 days or within a year for cases of childhood stroke)[19,20] and follow them and their families during their illness to determine the impact on quality of life.

5.2. Secondary objectives

Determine the impact of varicella on healthcare use, financial and health impact on family unit

6. STUDY DESIGN

6.1. Summary of Study Design

This is a prospective observational cohort study with no active interventions nested within a routine surveillance programme.

6.2. Primary and Secondary Outcome Measures

6.2.1. Primary outcome measures

The primary outcome of the study is to calculate the loss of Quality Adjusted Life Years (QALYs) and financial cost attributable in the families of children with acute VZV infection. This will be measured by standard quality of life tools (EQ5D-5L[21] and CHU9[22] in children) and EQ5D-5L in adults.

6.2.2. Secondary outcome measures

We will collect data on disease severity using a previously validated assessment of symptoms tool[23] demographics, healthcare use, illness within the family unit and missed work / education days. We will

QoL-PoX-H (IRAS 240389) Protocol Version 1.5 (27/11/201)

estimate the financial and societal costs for families through a daily diary inquiring about medication use, additional childcare costs and days of work missed.

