6.3. Study Participants

6.3.1. Overall Description of Study Participants

As part of routine surveillance and our usual infection control procedures, parents of all children attending hospital are be asked about chickenpox or exposure within the last 21 days. [5] If they are admitted with 'stroke', then this time period will be varicella within the last 12 months. [19,20] As surveillance of severe complications, routine data will be recorded: nature of complication, length of stay, antibiotic and other drug use, imaging and pathology laboratory use. Patients identified within this surveillance group will be consented for inclusion into the QALY study.

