6.3.2. Inclusion Criteria

- Male or Female, attending hospitalaged less than 16 years old.
- Currently have chickenpox or have had it during the last 21 days (12m for stroke).
- Informed consent obtained from the parent(s) with assent in children >6 years.

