6.4.2. Informed Consent

The study will be conducted in accordance with the ICH Guideline for Good Clinical Practice (GCP), all applicable subject privacy requirements and the guiding principles of the Declaration of Helsinki.

[figure not shown]
Prior to enrolment and any study procedure, children's eligibility will be checked, and informed consent will be obtained. The parents or carers of participants must personally sign and date the informed consent form before any study specific procedures are performed and children over the age of six will be asked for assent. Written and verbal versions of the participant information and informed consent will be presented to the parents or carers detailing the exact nature of the study, the implications and constraints of the protocol. It will be clearly stated that they are free to withdraw from the study at any time for any reason without prejudice to future care, and with no obligation to give the reason for withdrawal.

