6.4.3. Study HRQoL Tool

Once consent is given, study personnel will provide a brief demographic questionnaire to the parent or guardian which will also ask them to score their child's HRQoL at the time of consent as well as retrospectively score their child's HRQoL prior to becoming illand if they are already recovering their HRQoL on the worst day of the illness. Parents will be given a brief demonstration and instructions of our diary system and asked to complete this daily (or alternate days) whilst in hospital (or receiving outpatient parenteral antibiotics / OPAT as part of hospital level care at home), weekly once discharged from hospital for one month and then monthly until their child's symptoms have completely resolved with a final contact again at six months. (figure 1) The diary will consist of illness severity questions and HRQoL questionnaires for the child and their parents taking less than 5 minutes to complete. Children over the age of 7 years will be able to fill out their own quality of life questionnaires themselves.

Parents will be offered reminder contact for the diary entries by phone / SMS / email, with the option of completing questions over the phone or internet.

We anticipate that for the families of children with severe disease as a result of varicella, engagement with the study aims will be high and with good communication and weekly reminders there should be limited dropout.

QoL-PoX-H (IRAS 240389)

Figure 1: Timing of diary entries.(*INPATIENT includes receiving outpatient parenteral antibiotics / OPAT as part of hospital level care at home)

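### The protocol describes no collection of family costs, missed work or pre-admission contacts between illness onset and consent, so unless the forms look back, these outcomes are understated relative to QALY loss

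*Protocol*

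**What the plan says.** - **Objective.** Section 5.2 sets the secondary aim: "Determine the impact of varicella on healthcare use, financial and health impact on family unit". The synopsis also treats family finances as secondary, while Section 6.2.1 places family financial cost within the primary outcome.
- **Source of family costs.** Section 6.2.2 says the study will "estimate the financial and societal costs for families through a daily diary inquiring about medication use, additional childcare costs and days of work missed". The sentence before it lists, as data to be collected, "demographics, healthcare use, illness within the family unit and missed work / education days", and names no instrument or period for them.
- **Start of data collection.** Section 6.4.2: "Prior to enrolment and any study procedure, children's eligibility will be checked, and informed consent will be obtained". Section 6.4.3 continues: "Once consent is given, study personnel will provide a brief demographic questionnaire to the parent or guardian". That form also takes the child's HRQoL now, before the illness and, if the child is already recovering, on the worst day. Parents are then shown the diary and "asked to complete this daily (or alternate days) whilst in hospital" or on outpatient parenteral antibiotics, then weekly for a month, then monthly until resolution, with a last contact at six months.
- **Entry window.** Section 6.3.2: "Currently have chickenpox or have had it during the last 21 days (12m for stroke".
- **Hospital data.** Under routine surveillance, Section 6.3.1 states that "routine data will be recorded: nature of complication, length of stay, antibiotic and other drug use, imaging and pathology laboratory use".
- **QALY window.** Section 8.2 counts QALY loss from the first clinical signs until the parents judge the child back to normal.

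**The concern.** The objective concerns the impact of varicella, which means the whole illness. As described, family costs are counted only from the day the diary is handed over. The first days at home can include parental absence, a child kept out of childcare or school, medicines bought and GP visits. The protocol describes no step that records any of these.

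Two things are at stake. Family cost and time lost would be biased low, and no later analysis can recover data that were never collected. QALY loss and family cost would also cover different stretches of the same illness, which matters if the two are used together in an economic evaluation. Section 4.1.2 (on HRQoL) itself notes that earlier UK work did not assess time off work and similar social costs, so this is a gap the study means to fill.

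**Working it through.** The protocol gives no figure on this point, so there is nothing of its own to reproduce. The check is a cross-reading, followed by an illustration of size.

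**Step 1: which source covers the period from onset to consent?**

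| Item | Described source | Covers onset to consent? |
|---|---|---|
| Child HRQoL | Enrolment form (6.4.3) | Yes, by recall of pre-illness and, if recovering, worst day |
| Medicines, extra childcare, work days missed | Diary (6.2.2), begun after consent (6.4.2, 6.4.3) | Not described |
| Education days missed | Listed in 6.2.2, instrument and period not stated | Not described |
| GP and other contacts before admission | Healthcare use listed in 6.2.2, instrument and period not stated | Not described |
| Length of stay, drugs, imaging, laboratory use | Routine surveillance (6.3.1), not tied to consent | Yes, in hospital |

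Section 3 lists an inpatient daily diary and a weekly home diary. It lists no retrospective cost form.

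**Step 2: do the windows match?** QALY loss starts at the first clinical signs (8.2). The diary starts at or after consent. The difference is the onset-to-consent interval, which may reach 21 days under 6.3.2 for children without stroke.

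**Step 3: how large could the gap be?** The protocol gives no onset-to-consent interval, so the following values are assumptions. Let *g* be days from onset to consent and *d* illness days after consent, with equal burden on each day. Share of illness days missed = *g* / (*g* + *d*).

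| *g* (days) | *d* = 7 | *d* = 14 |
|---|---|---|
| 2 | 2/9 = 22% | 2/16 = 12.5% |
| 5 | 5/12 = 42% | 5/19 = 26% |
| 10 | 10/17 = 59% | 10/24 = 42% |
| 21 (eligibility limit) | 21/28 = 75% | 21/35 = 60% |

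For context, Section 4.1.1 puts the rash at around five days until crusting. A child enrolled after that with a secondary complication could have passed the whole infectious rash period before the diary began. The last row is an eligibility maximum, not a typical case.

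**Step 4: is the diary's content consistent?** Section 6.4.3 describes the diary as illness severity and HRQoL questions. Section 6.2.2 has the same diary asking about medicines, childcare costs and work. The two descriptions do not agree.

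**The case against.** The strongest reply is that this argues from silence. The diaries and the enrolment questionnaire are separate documents and are not shown. Section 6.4.3 cannot be a full list of items, since it omits the cost questions that 6.2.2 places in the diary. The questionnaire may also hold content the protocol does not describe. A question about days off work since the rash began cannot be ruled out. This stands, and it makes the conclusion conditional on the forms. It does not remove the point, because the protocol sets out a look-back for HRQoL and none for costs.

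Several stronger readings are tempting, but the document does not support them:

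- **That everything before enrolment is lost.** Routine surveillance records length of stay, drugs, imaging and laboratory use, so in-hospital use before consent is covered. Daily census review (6.4.1) should also tend to shorten the wait from admission to consent.
- **That healthcare use and missed education days are collected only after consent.** Section 6.2.2 ties only the financial and societal costs to the diary. For the other items it leaves instrument and period open.
- **That up to 12 months of costs are missing for stroke.** The 12 months separate chickenpox from stroke and are an eligibility rule. How much is missing depends on the start date used for QALY loss in stroke, which Section 8.2 does not set separately.
- **That the percentages estimate the bias.** They rest on assumed intervals and count days, not money, work days or contacts.
- **That comparisons between complication types are distorted.** This would follow if the onset-to-consent interval differs by complication, which is plausible, but the protocol gives no figure.

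**Conclusion.** The point holds in conditional form. The protocol describes no collection of family costs, missed work or education, or pre-admission contacts between illness onset and consent. Unless the forms already ask, family cost and time lost are understated relative to the window used for QALY loss. The direction is downward. The size cannot be determined from the protocol: about 13% to 59% of illness days under the assumed gaps of 2 to 10 days, 7 to 14 illness days after consent, and equal burden per day.

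This is more than a missing detail that an analysis plan could supply, because the described method of collection itself produces the shortfall. It deserves an amendment, or, if the forms do look back, one sentence saying so.

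**What to change.** 1. **Check the forms.** If they already ask about the period from onset to consent, state this in Sections 6.2.2 and 6.4.3.
2. **If they do not, add dated recall items to the enrolment questionnaire**, running from the first clinical signs to consent (for stroke, from the same start date as is used for QALY loss). Cover work days missed by carers, school or childcare days missed by the child, medicines and extra childcare paid for, and GP, telephone and other contacts before admission.
3. **Define the cost and healthcare-use outcomes** as enrolment recall plus diary plus routine hospital data.
4. **Apply this to new enrolments.** For families already enrolled without these items, report costs as running from consent only, or show late recall separately as a sensitivity analysis. Late recall would not be short: the study period starts in March 2018, version 1.5 is dated November 2019, and the last scheduled contact is at six months, so some families may have no contact left.
5. **Reconcile the two descriptions of the diary** in Sections 6.2.2 and 6.4.3.

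The cost is a few questions on a form already completed at consent, and a minor amendment. The downside for new families is a short recall period, which the protocol already accepts for HRQoL.

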6.3. Study Participants

6.3.1. Overall Description of Study Participants

As part of routine surveillance and our usual infection control procedures, parents of all children attending hospital are be asked about chickenpox or exposure within the last 21 days. [5] If they are admitted with 'stroke', then this time period will be varicella within the last 12 months. [19,20] As surveillance of severe complications, routine data will be recorded: nature of complication, length of stay, antibiotic and other drug use, imaging and pathology laboratory use. Patients identified within this surveillance group will be consented for inclusion into the QALY study.

6.3.2. Inclusion Criteria

- Male or Female, attending hospitalaged less than 16 years old.
- Currently have chickenpox or have had it during the last 21 days (12m for stroke).
- Informed consent obtained from the parent(s) with assent in children >6 years.

6.3.3. Exclusion Criteria

Only those for whom admission is felt to be clinically unrelated to recent varicella (e.g. injuries / new malignant diagnosis) should be excluded from the study.

6.3.4. Screening Data

We would also like sites to inform us if they become aware of any children who die as a result of VZV during the study period. We feel it would be unequivocally unethical to attempt to directly recruit these families, however with anonymous information on the number of cases (if any) and the age at which it occurred would allow use to incorporate this important data into the final analysis. This data will be routinely gathered as part of the case screening for the study.

6.4. Study Procedures

6.4.1. Patient identification

Study teams will carry out daily review of the hospital census to prospectively identify potential patients with chickenpox or a secondary complication. These will include but not limited to patients with skin infections, haemorrhagic vesicular rash, disseminated purpura, staphylococcal scalded skin syndrome, cellulitis, abscess, pneumonia, osteomyelitis, septic arthritis, myositis, adenitis, fasciitis, hepatitis, severe anorexia/dehydration, eye involvement, neurological issues, haematological disturbances or Reye's syndrome.[5] Any patient identified though this method will be invited to join this Quality of Life study.

Treating clinician will be asked to categorise cases into confirmed / likely / possible due to VZ and severity as Mild / Mod / Severe.

QoL-PoX-H (IRAS 240389)

6.4.2. Informed Consent

The study will be conducted in accordance with the ICH Guideline for Good Clinical Practice (GCP), all applicable subject privacy requirements and the guiding principles of the Declaration of Helsinki.

[figure not shown]
Prior to enrolment and any study procedure, children's eligibility will be checked, and informed consent will be obtained. The parents or carers of participants must personally sign and date the informed consent form before any study specific procedures are performed and children over the age of six will be asked for assent. Written and verbal versions of the participant information and informed consent will be presented to the parents or carers detailing the exact nature of the study, the implications and constraints of the protocol. It will be clearly stated that they are free to withdraw from the study at any time for any reason without prejudice to future care, and with no obligation to give the reason for withdrawal.

